Full study protocol and statistical analysis plan

Official Title of the study:

Analysis of some heavy metals and some vitamins levels in maternal samples, fetal samples and breast milk for fetal growth restriction.

Date of the document:

May 2020.

Contents:

1. Participant Flow
2. Baseline Characteristics
3. Outcome Measures
4. Endpoints of the study
5. Limitations and Strengths
6. Certain Agreements
7. Results Point of Contact

1. Participant Flow

Recruitment Details

This observational case-control study will be conducted at the Department of Obstetrics and Gynecology, Cengiz Gokcek Public Hospital, Gaziantep, Turkey, between May 2020 and February 2021. The protocol was approved by the Ethics Committee for Clinical Research of Gaziantep University (reference no: 2020/131). The study strictly will be adhered to the principles of the Declaration of Helsinki. All subjects will be included in the study gave oral and written informed consent. 110 women were enrolled in the study in two groups.

Pre-assignment Details

The authors first will be assessed the recruited people to ensure meeting the inclusion and exclusion criteria. The inclusion criteria will be made according to the official documents.

Arm/Group Information *

There are two groups in the study.

Arm/Group Title *

Fetal growth restriction group

Control group

2. Baseline Characteristics

To detect significant difference between groups according to lead levels with a moderate effect size (Cohen's $d=0.6$), minimum required sample size was estimated as 45 for each group ($\alpha=0.05$, $1-\beta=0.80$). Power analysis was performed by using G power package version 3.1. Kolmogorov Smirnov and Shapiro Wilk tests will be used to test the normal distribution of data. For comparing groups (FGR/control) the student t-test will be used for variables that have a normal distribution, and the Mann Whitney U test will be used for variables that have not a normal distribution. The ROC analysis will be applied for the determination of cut-off point for variables. Moreover, Spearman correlation test will be used for the relationship of between variables. SPSS for Windows 22.0 and Medcalc programs will be used for statistical analysis. $p<0.05$ will be accepted as statistical significance.

3. Outcome Measures

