Primary Outcome Measures : tin (Sn), manganese (Mn), Vanadium (V), Magnesium (Mg), cobalt (Co), nickel (Ni), arsenic (As), chromium (Cr), cadmium (Cd), lead (Pb), mercury (Hg), antimony (Sb), aluminium (Al), zinc (Zn), copper (Cu), selenium (Se), iron (Fe), vitamin D, vitamin A, vitamin B12 and folate concentrations

Secondary Outcome Measures: composite neonatal outcome (infant weight at delivery, placental weight, neonatal intensive care unit hospitalization, and APGAR scores)

Tertiary Outcome Measures: obstetric ultrasound/doppler examination and fetal-maternal assessment

4. Endpoints of the study:

The primary outcome in these analyses will compare tin (Sn), manganese (Mn), Vanadium (V), Magnesium (Mg), cobalt (Co), nickel (Ni), arsenic (As), chromium (Cr), cadmium (Cd), lead (Pb), mercury (Hg), antimony (Sb), aluminium (Al), zinc (Zn), copper (Cu), selenium (Se), iron (Fe), vitamin D, vitamin A, vitamin B12 and folate concentrations in FGR group and control group.

5. Limitations and strengths:

Our study has some strengths. These metals will be measured blood, urine and hair samples. So, these measurements may not reflect the metals exposure levels only recent exposure and will reflect before and during pregnancy.

6. Certain Agreements

This work will be supported by the Scientific Research Project Fund of Yozgat Bozok University.

7. Results Point of Contact

Corresponding Author: [name], Department of Obstetrics and Gynecology, Cengiz Gokcek Women's and Children's Hospital, Gaziantep, Turkey, [contact]

Address: [name]

GSM: [contact]

[contact]

[contact]

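### Infant and placental weight are analysed as raw grams with no stated control for gestational age, so an analyte that varies with gestation can correlate with weight without any relation to growth

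*Combined protocol and SAP*

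**What the plan says.** Section 3 (Outcome Measures) gives the secondary outcome as a "composite neonatal outcome (infant weight at delivery, placental weight, neonatal intensive care unit hospitalization, and APGAR scores". No centile, z-score or reference chart is attached to either weight.

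Section 2 (Baseline Characteristics) holds the analysis plan:

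- Group comparisons: "For comparing groups (FGR/control) the student t-test will be used for variables that have a normal distribution", with Mann-Whitney U otherwise.
- Associations: "Spearman correlation test will be used for the relationship of between variables". The pairs of variables are not named.
- ROC analysis for cut-off points.

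None of these methods carries a covariate. Gestational age is not mentioned anywhere in the document, whether as a baseline variable, restriction, matching factor or adjustment. On eligibility, section 1 (Participant Flow) says only that "The inclusion criteria will be made according to the official documents". On the groups it says "There are two groups in the study", and no matching is described.

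**The concern.** The study is about fetal growth restriction, that is, size relative to gestational age. Raw weight at delivery mixes two things: how well the fetus grew and how long the pregnancy lasted. An unadjusted analysis of raw weight cannot separate them.

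Two uses of the weights are exposed. First, section 2 leaves the Spearman pairs open, so analyte-to-weight correlations are permitted. If an analyte's concentration changes with gestation, it will tend to correlate with weight even when it has no bearing on growth. The plan lists 21 analytes and does not state at what gestation samples are taken, so it would be unsafe to assume that none of them varies with gestation. Second, if the two groups deliver at different gestations, part of the between-group difference in raw weight reflects timing.

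At stake is the reading of the secondary results: a significant analyte-weight correlation could be reported as evidence about growth when it reflects date of delivery. The mechanism can operate within each group, so it is separate from the fact that infant weight overlaps with case status.

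**Working it through.** **The plan's own figure.** Section 2 states that the "minimum required sample size was estimated as 45 for each group", for Cohen's d = 0.6, alpha 0.05 and power 0.80. A two-sided noncentral-t calculation gives exactly 45 (power 0.804; 44 per group gives 0.795). The figure reproduces. It concerns lead and does not use the weights, so this point leaves it unchanged.

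**Inputs for the check.** From the documents: 110 women in total, significance at 0.05, Spearman correlation, no covariates. Assumed, because the documents give no figures: late-pregnancy weight gain b = 150-200 g/week, SD of gestational age at delivery s = 1-2 weeks, SD of weight at a fixed gestational age 400 g, and analyte-gestational age correlation r = 0.2, 0.3 or 0.5. The analyte has no relation to weight at a given gestational age.

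**Step 1: share of raw-weight variance due to gestational age.** Share = (b·s)² / ((b·s)² + 400²).

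| b (g/week) | s (weeks) | (b·s)² | Share |
|---|---|---|---|
| 150 | 1 | 22,500 | 22,500/182,500 = 12% |
| 200 | 1 | 40,000 | 40,000/200,000 = 20% |
| 150 | 2 | 90,000 | 90,000/250,000 = 36% |
| 200 | 2 | 160,000 | 160,000/320,000 = 50% |

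**Step 2: induced correlation.** With no direct relation, the expected analyte-weight correlation is r(analyte, gestational age) × r(gestational age, weight), where the second factor is the square root of the share (0.35 to 0.71). For r = 0.5 this gives 0.5 × 0.35 = 0.18 at the mildest setting and 0.5 × 0.71 = 0.35 at the strongest.

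**Step 3: how often Spearman is then significant.** Simulated, with several thousand datasets per setting. Ranges run from the mildest to the strongest row of step 1.

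| Analyte-gestational age r | One population, n = 110 | One group, n = 55 | Gestational age removed |
|---|---|---|---|
| 0.2 | 11-29% | 7-16% | about 5% |
| 0.3 | 18-57% | 12-31% | about 5% |
| 0.5 | 42-95% | 23-72% | about 5% |

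The n = 55 column assumes an even split (110/2), which the document does not state.

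**Step 4: a second parameterisation.** Setting the correlations directly, with r(analyte, gestational age) = 0.3 and r(gestational age, weight) = 0.7, the expected value is 0.21. The raw test is significant in 56% of studies of 110, against 5.6% after partialling on gestational age. With r(analyte, gestational age) = 0, the raw test stays at about 5%.

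**Step 5: group comparison.** If mean gestation at delivery differed by one week (assumed), 150-200 g of the raw-weight difference between groups would be timing alone.

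Placental weight was not simulated. The same reasoning applies to the extent that it rises with gestation.

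**The case against.** The strongest reply is that the faulted analysis is not written down. No analyte-to-weight correlation is specified. The weights appear as part of a neonatal outcome beside intensive care admission and Apgar scores, not as growth measures, and growth status enters through the case-control grouping. Raw birthweight is a legitimate descriptor. All of this is fair and makes the point conditional. It does not remove it, because the weights are listed outcomes and nothing excludes them from the Spearman tests.

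A second reply is that the eligibility documents referred to in section 1 may restrict or match on gestational age. That is possible. It cannot be concluded that gestational age is uncontrolled, only that no control is stated here. Restriction would shrink the spread and hence the bias, without necessarily removing it.

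A third is that a single homogeneous population of 110 is not this design. That also stands. Within a group of 55 the rates are lower. Pooling two groups assumed to be 800 g apart, with the same gestational-age distribution, gives about 8-19%, 11-40% and 24-83%. The mechanism survives, but the upper end of the n = 110 range should not be quoted as the expected rate.

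Two stronger readings are tempting and unsupported. A reader might infer that any association of an analyte with weight is partly timing; step 4 shows that this needs an analyte that varies with gestational age. A reader might also infer that a normally grown infant born early will always weigh less than a restricted infant born near term; that depends on how early and how restricted, and the documents give no figures.

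**Conclusion.** The point holds in conditional form. As written, the plan analyses raw infant and placental weight with unadjusted tests and states no control for gestational age. If those weights are correlated with analytes, one that varies with gestational age at delivery can give a significant result unrelated to growth. If the groups deliver at different gestations, their weight comparison is distorted as well.

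Under the stated assumptions gestational age makes up about 12-50% of raw-weight variance. Even at the mildest setting with r = 0.2, the false-positive rate at n = 110 is about twice the nominal 5%. Every magnitude rests on assumed weight gain, spread and correlations. The documents supply only the sample size, the significance level and the test.

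It should not be inferred that the main result is compromised. The primary endpoint in section 4 compares analyte concentrations between groups and does not use these weights. This is a secondary-outcome fault that is cheap to correct.

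**What to change.** In section 3, define infant weight as a birthweight z-score for gestational age and sex, from one named reference chart. Define placental weight as weight for gestational age, or analyse it adjusted for gestational age at delivery. Keep raw grams for description.

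In section 2, name the analyte-weight pairs. Run these correlations within each group, or as partial correlations adjusted for group, using the standardised weights or adjusting for gestational age at delivery. State whether eligibility restricts or matches on gestational age.

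Two cautions apply. The placental-to-birthweight ratio should not be relied on to remove gestational age, since it does so only if both weights rise in proportion, which is not shown. A z-score association pooled across groups should not be read as separate from case status, because growth restriction is itself size for gestational age and the pooled score would largely restate the grouping.

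The cost is naming one chart, deriving one variable and revising a few sentences. Gestational age is needed to diagnose growth restriction and sex is known at birth, so little or no new data collection should be needed. The sample size does not change.

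### Twenty-one unranked primary analytes, none tied to a specimen, are each tested at an unadjusted 0.05: if none differs, the chance of at least one false positive is 66% under independence and 16% at an assumed correlation of 0.9

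*Combined protocol and SAP*

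**What the plan says.** Section 3 (Outcome Measures) opens its list with "Primary Outcome Measures : tin (Sn), manganese (Mn), Vanadium (V), Magnesium (Mg), cobalt (Co), nickel (Ni". Section 4 (Endpoints of the study) repeats the same list as a between-group comparison, beginning with "The primary outcome in these analyses will compare tin (Sn), manganese (Mn), Vanadium (V), Magnesium (Mg), cobalt (Co), nickel (Ni" and ending with "selenium (Se), iron (Fe), vitamin D, vitamin A, vitamin B12 and folate concentrations in FGR group and control group". Neither section ranks the analytes or says in which specimen a concentration is to be measured.

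The statistical methods are in section 2 (Baseline Characteristics). Testing is variable by variable: "For comparing groups (FGR/control) the student t-test will be used for variables that have a normal distribution", and otherwise "the Mann Whitney U test will be used for variables that have not a normal distribution". The threshold is "p<0.05$ will be accepted as statistical significance". The document contains no Bonferroni, Holm, false-discovery-rate, gatekeeping or global-test provision.

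Lead is singled out only for sizing: "To detect significant difference between groups according to lead levels with a moderate effect size" (Cohen's d of 0.6, alpha 0.05, power 0.80), from which "minimum required sample size was estimated as 45 for each group".

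Specimens are mentioned in two other places, which do not match. The study title refers to maternal samples, fetal samples and breast milk. Section 5 (Limitations and strengths) refers to blood, urine and hair, and only for the metals. Neither assigns a specimen to a primary comparison.

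**The concern.** Each single test keeps its own 5% error rate. The difficulty is the statement that at least one primary analyte is associated with fetal growth restriction. The plan leaves that statement available, because every analyte is primary, one significance rule covers them all, and the study is nowhere called exploratory. If no analyte differs, such a statement would be wrong far more often than 5% of the time.

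The open specimen makes this worse. A reader shown all 21 results from one specimen could count them and adjust. With several specimens possible and none specified, the reader cannot tell how many primary tests were planned, or whether the reported specimen was chosen after the results were known.

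The sample size is also affected. It was derived for one test at 0.05, so its 80% power does not carry over to a family of 21 tested at an adjusted level.

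**Working it through.** **Inputs.** From sections 3 and 4: Sn, Mn, V, Mg, Co, Ni, As, Cr, Cd, Pb, Hg, Sb, Al, Zn, Cu, Se and Fe (17), plus vitamins D, A, B12 and folate (4), so m = 17 + 4 = 21. From section 2: alpha 0.05, d = 0.6, power 0.80, 45 per group. From section 1: 110 women in two groups; the split is not given, so 55 per group is an assumption. Correlations between analytes are not given, so a range is assumed.

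**1. The plan's own figure.** Two-sided two-sample t-test, n per group, noncentrality d·√(n/2), 2n − 2 degrees of freedom. At n = 44 the power is 79.5%. At n = 45 the noncentrality is 0.6 × √22.5 = 2.846 and the power is 80.4%. The stated 45 per group reproduces. At 55 per group the power is 87.7%.

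**2. Family-wise error, independent tests.** 1 − 0.95^21 = 1 − 0.341 = 0.659, or 66%. The expected number of false positives is 21 × 0.05 = 1.05, whatever the correlation.

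**3. Family-wise error, correlated tests.** Assume all 21 null hypotheses true and test statistics sharing a common correlation r. With φ and Φ the standard normal density and distribution function and c = 1.96,

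P(at least one) = 1 − ∫ φ(u)·[Φ((c − √r·u)/√(1−r)) − Φ((−c − √r·u)/√(1−r))]^m du.

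The second row of results assumes all 17 metals tested in blood, urine and hair and each vitamin once: 17 × 3 + 4 = 55 tests.

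| r | 0 | 0.3 | 0.5 | 0.7 | 0.9 | 0.99 |
|---|---|---|---|---|---|---|
| 21 tests | 66% | 55% | 43% | 30% | 16% | 8% |
| 55 tests (assumed) | 94% | 83% | 64% | 42% | 20% | 8% |

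A simulation of 21 two-sided t-tests at 45 per group (20,000 replicates) gave 66.7% at r = 0 and 15.7% at r = 0.9, in agreement.

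**4. Power for lead after adjustment.** At Holm's first step the level is 0.05/21 = 0.00238, or 0.05/55 = 0.00091 for the assumed larger family. The t-test figures are from the noncentral t. The Mann-Whitney figures are from simulation with normal data.

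| Level | t, 45/group | t, 55/group | Mann-Whitney, 45 | Mann-Whitney, 55 |
|---|---|---|---|---|
| 0.05 | 80.4% | 87.7% | 78% | 86% |
| 0.05/21 | 39.5% | 51.6% | 36% | 48% |
| 0.05/55 | 29% | 40% | 25% | 36% |

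The adjusted figures are lower bounds under Holm, because later steps are less strict. Restoring 80% power by t-test at 0.05/21 would take 86 per group. For non-normal data, Mann-Whitney power depends on the shape of the distribution, which the documents do not give.

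**The case against.** The strongest reply is that the plan never says the study succeeds if any one analyte differs. It says only that 21 concentrations will be compared. In an observational case-control study with no treatment decision attached, 21 separate questions each answered at 5% is a position some statisticians would defend, and the choice between that and family-wise control is partly a matter of judgement. This tempers how severe the defect looks but does not remove it. The plan labels all 21 primary, sets a formal significance rule and a power calculation, and does not describe itself as exploratory. If separate or exploratory questions were intended, the plan has to say so and fix the specimens.

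The percentages also require all 21 null hypotheses to be true and, away from independence, one common correlation. That is right, and it is why a range is shown. The error exceeds 5% at every value tried.

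It can also be said that specimens are named. They are, in the title and in section 5; what is missing is any link from a specimen to a primary comparison.

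Finally, adjusting comparisons that are openly labelled exploratory is not obligatory. Clear labelling with full reporting would also be defensible.

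**Conclusion.** The concern holds and needs to be corrected before the analysis. Followed as written, with each analyte tested once and none differing, the plan gives a 66% chance of at least one significant primary result under independence. Under an assumed common correlation the figure is 43% at 0.5 and 16% at 0.9. Several specimens per metal would raise it, to 64% and 20% at those correlations in the assumed 55-test family. That there is no adjustment is inferred from the document's silence, but the document presents itself as the full protocol and SAP. The sample size calculation is correct for what it addresses, a single two-sided t-test on lead, and does not support 21 primary endpoints at an adjusted level.

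**What to change.** Before any group comparison is seen, adopt one of the following. Under either, list the specimens collected for each analyte.

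**(a) One primary endpoint.** Name one analyte in one stated specimen, tested two-sided at 0.05. Lead is the natural candidate because the sample size rests on it, but the choice is the investigators'. All other analyte-by-specimen comparisons become secondary, under Holm or Benjamini-Hochberg, or are labelled exploratory and reported in full. If lead is chosen, the planned power stands, with the slightly lower Mann-Whitney figure stated alongside.

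**(b) Keep all 21 primary.** Name the specimen for each and apply Holm across the whole family. Use a false-discovery-rate procedure only if the plan says that this, and not the family-wise error, is what it controls. State that 80% power for lead no longer holds, and give the adjusted figures for the family actually fixed.

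If group results have already been seen, option (b) applies, with that fact disclosed and every specimen already compared included in the family.

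**Cost.** No extra patients or assays, provided that the lower power under (b) is accepted. Under (a), 20 analytes lose primary status. Under either, some nominally significant analytes may no longer be declared significant. The choice must be dated relative to the first group comparison, because section 1 reports enrolment of the 110 women in the past tense while most of the plan is written in the future.

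### No specimen is named for the 21 primary concentrations or for the powered lead comparison, so with every test judged at p<0.05 a chance result in any analyte and specimen can count as primary.

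*Combined protocol and SAP*

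**What the plan says.** Five places in the combined protocol and SAP bear on this.

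- **Official title.** It refers to "levels in maternal samples, fetal samples and breast milk for fetal growth restriction". It does not say which maternal or fetal samples are meant.
- **Section 2, Baseline Characteristics.** The sample size is calculated "To detect significant difference between groups according to lead levels", with d=0.6, alpha 0.05 and power 0.80, giving 45 per group. No specimen, mean, SD or unit is given for lead. The same section sets p<0.05 as the significance threshold and states no adjustment for multiple tests.
- **Section 3, Outcome Measures.** The primary list has 17 elements followed by "vitamin D, vitamin A, vitamin B12 and folate concentrations", 21 analytes in all, with no specimen.
- **Section 4, Endpoints of the study.** The same 21 analytes are compared between groups; the sentence ends "vitamin B12 and folate concentrations in FGR group and control group". Again no specimen is named.
- **Section 5, Limitations and strengths.** "These metals will be measured blood, urine and hair samples". It does not say whether these come from mother or fetus, does not mention breast milk, and covers the metals only.

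Nothing in the document links an analyte to a specimen or ranks one specimen above another.

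**The concern.** A concentration in blood, in urine, in hair and in milk are different variables. Section 5 relies on this itself: it counts the range of specimens as a strength because it should capture exposure before and during pregnancy as well as recent exposure. A plan that treats specimen as meaningful has to say which specimen carries the primary comparison.

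Without that, two things are lost. First, a reader of the results cannot tell whether the specimen reported as primary was fixed in advance or picked because it gave p<0.05. Second, the one comparison that was powered, lead, cannot be matched to a single planned test. The missing specimen also multiplies a problem that is already there, namely 21 primary analytes tested with no error control.

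**Working it through.** **Inputs.** From section 2: d=0.6, alpha 0.05, power 0.80, 45 per group, 110 women in two groups, threshold p<0.05. From sections 3 and 4: 17 elements + 4 vitamins = 21 analytes. From section 5: three specimens, for metals.

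**Step 1: reproduce the sample size.** By the normal approximation, n per group = 2(z₀.₉₇₅ + z₀.₈₀)²/d² = 2(1.960 + 0.842)²/0.36 = 43.6, so 44. The noncentral t solution is 44.59, so 45, which matches the plan; power at 45 per group is 0.804. A one-sided test would need 35.04, so 36, which does not match. The stated figure is therefore a two-sided t-test at 0.05.

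**Step 2: can the calculation show which specimen was meant?** No. The effect is standardised (d = mean difference/SD) and no lead mean, SD or unit is given. The same 45 results for lead in any specimen.

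**Step 3: compare the two specimen lists.**

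| Specimen | Title | Section 5 |
|---|---|---|
| Breast milk | named | absent |
| Blood, urine, hair | not named, but could fall under maternal or fetal samples | named, source not stated |

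Only breast milk is clearly unmatched.

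**Step 4: count the primary tests the text permits.** If all null hypotheses are true and m tests are each run at 0.05, the expected number of false positives is 0.05m, and for independent tests the chance of at least one is 1 − 0.95^m.

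| Reading | m | Expected | Chance of at least one |
|---|---|---|---|
| One specimen per analyte | 21 | 1.05 | 1 − 0.95²¹ = 65.9% |
| 17 elements × 3 specimens + 4 vitamins × 1 | 55 | 2.75 | 1 − 0.95⁵⁵ = 94.0% |
| Lead only, 3 specimens | 3 | 0.15 | 1 − 0.95³ = 14.3% |

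The second row is an assumption: the documents do not say that all 17 elements are measured in all three specimens, or that the vitamins are measured in one.

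**Step 5: separate the two sources.** The 66% arises from having 21 analytes and would be the same if one specimen were named. What the unnamed specimen adds is the step from 21 to 55 tests (66% to 94%) overall and, for the powered variable, the step from 5% to 14.3%.

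**Step 6: what 45 per group covers.** It gives 0.804 for lead in one specimen. As an illustration, if lead in three specimens were co-primary at 0.05/3 with d=0.6 in each, 60 per group would be needed (59.61 rounded up). Power per specimen would be 65.7% at 45 per group, or 76.1% at 55 per group if the 110 women split equally, which the plan does not state.

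**The case against.** The strongest reply is that this is an omission and not a conflict. The title mostly sorts samples by source and section 5 by type; maternal samples may well be blood, urine and hair. Section 5 is a remark about strengths, covers only the metals and does not claim to be complete. That stands. A reader might infer that the title and section 5 contradict each other outright, but the wording supports only one unmatched specimen, breast milk.

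It can also be said that most of the false-positive risk comes from the 21 analytes and not from the specimens. That stands too, and Step 5 separates the two.

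Two further inferences are tempting and should be resisted. One is a larger test count, built by adding fetal blood and breast milk to the section 5 list. No section names fetal blood or says which analytes would be measured in milk, so such a count is a construction. The other is that true power for lead is far below 0.80 because a Bonferroni correction across all the analytes would reduce it. The plan applies no such correction, and at its own two-sided 0.05 the 45 per group delivers what it states for lead in any one specimen.

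None of this identifies the primary specimen. The reply narrows the point but does not answer it.

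**Conclusion.** The point holds as a defect of endpoint specification, not of arithmetic, and it must be fixed because the primary comparison cannot be identified from the plan. The minimum reading already allows about one false-positive primary result by chance. That expectation does not need independence, only that the null hypotheses are true. The 66%, 94% and 14% do assume independent tests; positive correlation between analytes or between specimens would generally lower them. The 55-test figures also rest on the assumed allocation of analytes to specimens.

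A reader might conclude that the stated power describes no test at all. That goes too far: the test is lead, growth-restricted group against control, by a two-sided t-test at 0.05. What is missing is the specimen.

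**What to change.** 1. Reconcile the title and section 5 into one list of specimens, stating whether each comes from mother or fetus and which analytes are measured in it. Breast milk should either be added to section 5 or removed from the title.
2. In section 4, make lead in one named specimen the single primary comparison at two-sided 0.05, and name the same specimen in the sample size paragraph. The 45 per group then stands unchanged.
3. Choose that specimen, and document the choice with a date, before any group data are examined. The specimen behind d=0.6 may not be recoverable, since the plan calls it only a moderate effect. The plan mixes tenses about enrolment, so it is unclear how far the study had progressed. If group data have already been seen, say so and do not present the choice as prespecified.
4. Make every other analyte-specimen pair secondary, with Benjamini-Hochberg control at 5% across the whole set of pairs. Control within each specimen separately would leave multiplicity across specimens open.

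This needs no extra women or samples, only a change to the plan and a dated record of the choice. The cost is that the other 20 analytes, none of which was powered, lose primary status and face a stricter threshold. For a single isolated finding that threshold would be 0.05/20 = 0.0025 with one specimen per analyte, or 0.05/54 ≈ 0.0009 on the 55-test reading.

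### Metals are to be measured in urine and concentrations compared with unadjusted tests, but no dilution correction or timed collection is specified

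*Combined protocol and SAP*

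**What the plan says.** Urine appears once, in section 5 (Limitations and strengths) of the combined protocol and SAP: "These metals will be measured blood, urine and hair samples". That section presents the choice of specimens as a strength.

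Section 4 (Endpoints of the study) defines the primary outcome as a comparison of 17 metals and four vitamins, ending "vitamin A, vitamin B12 and folate concentrations in FGR group and control group". It gives no specimen type, unit or denominator.

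The analysis is described in section 2 (Baseline Characteristics): "For comparing groups (FGR/control) the student t-test will be used for variables that have a normal distribution", with Mann-Whitney U otherwise. ROC analysis for cut-offs and Spearman correlation between variables follow. There is no covariate or adjustment.

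The sample-size statement is in the same section: "To detect significant difference between groups according to lead levels with a moderate effect size" (Cohen's d of 0.6, alpha 0.05, power 0.80), "minimum required sample size was estimated as 45 for each group". Section 1 (Participant Flow) states "110 women were enrolled in the study in two groups".

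No section mentions urinary creatinine, specific gravity, osmolality, timed or 24-hour collection, or any other handling of urine dilution.

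**The concern.** The concentration of a metal in a spot urine sample is the amount excreted divided by the urine volume over the same interval. Fluid intake changes the volume without changing exposure, so part of the variation between women is hydration. Neither group test removes it. Mann-Whitney U deals with skewness, not with a nuisance factor shared by every metal in the sample.

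All three planned analyses would be affected for urine:

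- **Group comparison.** Dilution adds variance and lowers power. If average dilution differs between FGR and control women, all 17 urine metals shift in the same direction, and the result would look like a consistent exposure pattern.
- **Spearman correlation.** A shared dilution factor makes unrelated urine metals correlate positively.
- **ROC cut-offs.** A cut-off on uncorrected urine concentration partly classifies hydration.

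**Working it through.** **Inputs from the documents.** d = 0.6 for lead (specimen not stated), alpha 0.05, power 0.80, 45 per group (section 2); 110 enrolled (section 1), which is 55 per group if split equally, although the split is not stated.

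**Inputs assumed.** Urine samples are spot samples. On the log scale, measured concentration is the metal signal plus an independent dilution term. Let r be the dilution SD divided by the metal SD, taken from 0.25 to 1.0. For the false-difference calculation, let s be the total SD of log concentration, taken from 0.5 to 1.0. None of these values is in the documents.

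**Step 1: the plan's own figure.** A two-sided two-sample t-test with d = 0.6, alpha 0.05 and power 0.80 needs 44.6, so 45 per group; power at 45 is 0.804. The stated figure reproduces. At 55 per group, power is 0.877.

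**Step 2: noise.** If 0.6 is the effect after dilution is removed, the effect on uncorrected values is d_raw = 0.6 / √(1 + r²). For r = 1.0 this is 0.6 / √2 = 0.424. Power is from the noncentral t.

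| r | d_raw | Power, 45 per group | Power, 55 per group |
|---|---|---|---|
| 0 (corrected) | 0.600 | 0.804 | 0.877 |
| 0.25 | 0.582 | 0.780 | 0.857 |
| 0.50 | 0.537 | 0.711 | 0.796 |
| 0.75 | 0.480 | 0.615 | 0.704 |
| 1.00 | 0.424 | 0.512 | 0.597 |

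**Step 3: induced correlation.** Two urine metals that are truly independent and share the dilution term have log-scale correlation r² / (1 + r²). For r = 0.25 this is 0.0625 / 1.0625 = 0.06; for r = 1.0 it is 1 / 2 = 0.50. This is the product-moment correlation; under normality the Spearman value is slightly lower at the upper end (0.48).

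**Step 4: false difference.** Suppose there is no true difference in the metal, but urine is more concentrated in one group by a ratio q. The spurious effect is d = ln(q) / s. With q = 1.2, ln(1.2) = 0.182.

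| s | Spurious d | P(p < 0.05), 45 per group | P(p < 0.05), 55 per group |
|---|---|---|---|
| 0.5 | 0.365 | 0.40 | 0.47 |
| 0.7 | 0.260 | 0.23 | 0.27 |
| 1.0 | 0.182 | 0.14 | 0.16 |

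With q = 1.1 the rejection probability at 45 per group is 0.07 to 0.15. The nominal rate is 0.05 throughout.

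**The case against.** Most of the case on the other side is right, and it limits the point.

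- **A reader might infer that the plan has decided to compare uncorrected urine values.** It has not said so. The absence of correction is read from silence; the laboratory may correct for dilution already. What stands is that a document titled as the full protocol and SAP specifies none.
- **A reader might infer that urine is part of the primary comparison.** Section 4 names analytes and no specimen, and the study title names only maternal samples, fetal samples and breast milk. Section 5 offers urine as a specimen for these metals and nothing excludes it, so its role is open, not established.
- **A reader might infer that the study is underpowered or that 45 per group is wrong.** The documents do not support that. Cohen's d is scaled by the SD of whatever is measured, and 0.6 is for lead with no specimen named. If it refers to blood, or to urine as measured, power stays at 0.80. The loss in Step 2 arises only if 0.6 is a dilution-free urine effect.
- **The false-difference figures are conditional.** Nothing in the documents suggests that hydration differs between FGR and control women. The rates also depend on both s and the number per group, so they cannot be quoted as one range across sample sizes. They do not follow from r either: if dilution varies little between women, a 20% group difference is a large one. With r = 0.25 and s = 0.5 the dilution SD is 0.5 × 0.25 / √1.0625 = 0.121, so 0.182 is 1.5 dilution SDs.
- **Silence on dilution is one part of a wider gap.** Specimen, unit and collection are undefined for every endpoint. That is true, but defining them would not by itself settle dilution, which concerns urine specifically and has its own remedy.

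One further limit: dilution correction does not deal with differences in how the kidney handles a particular metal, and no such claim is made here.

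**Conclusion.** The point holds for urine metals only, and it is minor. Section 5 puts the metals in urine, section 4 compares concentrations, and section 2 supplies only unadjusted methods. Followed as written with spot samples, the plan carries hydration variation into every urine result.

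The noise and the induced correlations need only that dilution varies between women. The false group difference needs, in addition, that average dilution differs between the groups. For the assumed ranges the power loss runs from slight (about 2 percentage points at r = 0.25) to serious (about 29 points at r = 1.0, at 45 per group). All magnitudes are illustrations. Blood, hair, the vitamins and the sample-size calculation are not affected.

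**What to change.** 1. State how urine is collected, and whether the laboratory already corrects for dilution. If it does, a sentence giving the method settles the point.
2. If it does not, measure specific gravity (or creatinine) in each urine sample. Compare dilution-standardised log urine metals between groups, or model log metal with the dilution marker as a covariate. Use the same values for the Spearman and ROC analyses, and report uncorrected values as a sensitivity analysis.
3. If creatinine is used, check that it does not itself differ between FGR and control women; otherwise the correction could introduce a difference of its own.
4. If no marker can be obtained, state that urine results are exploratory and not part of the primary comparison.

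Fixing the choice before results are seen also prevents later selection between corrected and uncorrected values. The cost is one inexpensive routine reading per urine sample, provided that sample is still available, which the documents do not state. Item 4 costs wording only. No extra visit is needed.
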